## **1.8.8 Exploratory analyses**

### **Psoriatic arthritis**

Summary statistics will be provided for HAQ-DI score and HAQ-DI response over time for all subjects with psoriatic arthritis recorded on the Psoriatic Arthritis History eCRF at screening.

### **1.8.9 Biomarkers**

Not applicable.

### **1.8.10 Health-related Quality of Life (HRQoL)**

Summaries will be based on the FAS and will be presented separately for study periods if not specified otherwise.

#### **Dermatology Life Quality Index**

The DLQI measures functional disability of subjects with dermatological disorders that are greater than 18 years of age and had been utilized as a relevant clinical measure in atopic dermatitis, as well as other dermatitis clinical trials. The DLQI is a simple, validated, self-administered 10-item questionnaire. The instrument contains six functional scales (i.e., symptoms and feeling, daily activities, leisure, work and school, personal relationships, treatment). For the DLQI, each question will be answered with the following response: “not at all,” “a little,” “a lot,” or “very much”. Seven scores will be derived from the DLQI: the total score of each of the six dimensions as well as the total score over all items. The higher the score, the more quality of life is impaired.

In addition, summary statistics will be provided for number of subjects achieving DLQI 0 or 1.

Output shells in MAP module 7.1: T\_DLQIANA3

## EQ-5D

The EQ-5D is a questionnaire with 5 questions each with three categories (no problem, moderate problem, severe problems) and a health state assessment from 0 (worst possible health state) to 100 (best possible health state). The number and percentage of subjects in each of the three categories for each question will be presented by analysis visit and treatment group.

Summary statistics will be shown for the health state assessment by analysis visit and treatment group.

### **HAQ©-DI (for subjects with PSA at baseline of the core study)**

Summary statistics will be derived for HAQ©-DI score over time for all subjects with psoriatic arthritis recorded on the Psoriatic Arthritis History eCRF at screening visit of the core study.

Absolute and relative frequencies for HAQ©-DI response will also be presented. HAQ©-DI response is defined by an improvement of 0.3 score points compared to baseline.

## **1.9 Standard safety evaluation**

All safety analyses will be based on the safety set. Core study baseline will be used for all change from baseline analysis.

Absolute and relative frequencies and exposure time adjusted incidence rate or event rate analysis will consider all the events (AEs/SAEs and clinically significant newly occurring lab, vitals and ECG abnormalities) that occurred in core studies and extension study for entire treatment period and in extension study for treatment period in E1.

Safety analyses will be performed on treatment received or actual treatment (See [Section 1.2](#)).

### **1.9.1 Adverse events**

Treatment emergent adverse are defined as events started after the first dose of study medication or events present prior to the first dose of study medication but increased in severity after dosing based on preferred term and within last dose + 84 days or last visit date of follow-up 1 period which comes earlier. Only treatment emergent adverse events are summarized

The crude incidence of treatment emergent adverse events will be presented for the entire treatment period and also by yearly interval (365 days) for 150 and 300 mg FI cohorts. The crude incidence of treatment emergent adverse events will be summarized by primary System Organ Class (SOC) and Preferred Term (PT). Confidence intervals for the crude rate will be derived as described in [Section 2.3.1](#). In addition, exposure time-adjusted incidence rates including 95% confidence intervals will be provided for the entire treatment period by yearly interval (365 days) for 150 and 300 mg FI cohorts.

Please note that exposure adjusted incidence rates will be provided and follow the guideline as below:

- Primary SOC level for AE and SAE
- Level 1 for risks and SMQ

- PT level for SAE
- PT level for AE  $\geq$  2%, or events that had an incidence rate of at least 5.0 cases per 100 subject-years in one of any AIN457 XXX mg
- Other selected AEs on lower levels (e.g. PT or SMQ level 2), if appropriate
- Special AE interest:
- 

| Special AE interest:  | Notes (All levels are displayed)                           |
|---|--|
| Inflammatory bowel disease (NMQ) (narrow)                     | Include Crohns (PT) and Ulcerative colitis (PT) and others |
| Opportunistic infections (NMQ)                                |  |
| Candida infections (HLT)                                      |  |
| Herpes viral infections (HLT)                                 | Both Oral and other are included                           |
| Staphylococcal infections (HLT)                               |  |
| MACE (MI, Stroke, Cardiovascular death) (NMQ)                 |  |
| Cardio-cerebrovascular-related events (NMQ)                   |  |
| Malignant or unspecified tumours (SMQ)                        | Including BCC, SCC in SMQ                                  |
| Malignant or unspecified tumours (SMQ excl BCC and SCC) (NMQ) |  |
| Upper respiratory tract infections (HLT)                      |  |

Adverse events will be summarized by presenting, for each treatment group (including “any AIN457”), the number and percentage of subjects having at least one AE at each year interval (for 150 and 300 mg FI cohorts), having an AE in each primary system organ class and having each individual AE (preferred term). Summaries will also be presented for AEs by severity and for study treatment related AEs. If a particular AE ‘severity’ is missing, this variable will be listed as missing and treated as missing in summaries. If a subject reported more than one adverse event with the same preferred term, the adverse event with the greatest severity will be presented. If a subject reported more than one adverse event within the same primary system organ class, the subject will be counted only once with the greatest severity at the system organ class level, where applicable.

The most common adverse events reported ( $\geq$  z % in any group for each preferred term in the table by SOC and PT or  $\geq$  z % in any group for each SMQ table) will be presented in descending frequency according to its incidence in total secukinumab group (combining all secukinumab treatment groups) starting from the most common event. Here threshold value z is set to 1 (%) but it may be updated following review of the dry run outputs.

Adverse events that started in core studies before the first dose of the study treatment in extension and continued into extension will not be included in the on treatment in E1 tables. Separate summaries will be provided for deaths, serious adverse events, other significant adverse events leading to discontinuation and adverse events leading to dose adjustment.

Adverse events will also be summarized by SMQ according to MedDRA.

Exposure time will be derived as following:

- Starting day: is the first study day of each period (Day 1 for year 1, Day 366 for year 1-2, etc.,)
- Ending day:
  - For patients with events: first AE onset day within each interval (worsening is not considered between the yearly interval) or first lab event assessment day
  - For patients without any event during the interval:
    - i. Censored day for AEs is defined as min [end of period day (i.e., day 365 for year 1, day 730 for year 1-2, etc.,), or min(last visit day, last dose + 84 days) for early discontinued subjects, or switched date]
    - ii. Censored day for Labs will be end of period day (i.e., day 365 for year 1, day 730 for year 1-2, etc.,) for ongoing patients or the last assessment day within each interval.

The MedDRA version used for reporting the adverse events will be described in a footnote. Listings of all adverse events will be done based on entire study period and follow-up 2 period separately. A column indicating if the adverse event is treatment emergent or not will be shown. Non-treatment emergent adverse events may be summarized separately upon request.

Algorithms for date imputations will be provided in RAP M8.

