If they refuse to return for the needed assessments in the follow-up period or are unable to do so, every effort should be made to contact them or a knowledgeable informant by telephone or by sending appropriate correspondence (i.e. certified letter) immediately. At this contact, the safety (e.g., potential occurrence of AE or SAE) and the primary reason for a subject's premature withdrawal should be determined.

At a minimum, subjects will be contacted for safety evaluations during the 12 weeks following the last dose of study treatment, including final contact at the 12-week point. Documentation of attempts to contact the subject should be recorded in the subject record.

Order of assessments:

- Subject to complete QoL tools prior to any investigator assessments. Order of QoL tools is: DLQI, EQ-5D, HAQ-DI (subjects with history of PsA only but not applicable to subjects from the CAIN457A2307 core study)
- Investigator to complete investigator assessments. Order is:

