9.5.2 Safety variables

All safety evaluations will be performed on the Safety set.

Adverse events

Treatment emergent adverse events are defined as any events started after the first dose of study treatment and within 84 days after the last study treatment, or events present prior to the first dose of study treatment, but increased in severity based on preferred term within 84 days after the last study treatment.

With the exception of adverse events that qualify as "treatment emergent" (see definition above), data collected from telephone visits and unscheduled visits in follow-up period 2 will only be included in individual patient listings, but not in summary tables.

AEs will be summarized by presenting, for each treatment group, the number and percentage of subjects having any AE, having an AE in each primary system organ class and having each individual AE (preferred term). Summaries will also be presented for AEs by severity and for study treatment related AEs. If a subject reported more than one adverse event with the same preferred term, the adverse event with the greatest severity will be presented. If a subject reported more than one adverse event within the same primary system organ class, the subject will be counted only once with the greatest severity at the system organ class level, where applicable.

Confidence intervals for relative frequencies will be derived as well according to the score method including continuity correction by [Newcombe, 1998](#).

Separate summaries will be provided for death, serious adverse event, other significant adverse events leading to discontinuation and adverse events leading to dose adjustment (including study treatment discontinuation).

A graphical display of relative frequencies within system organ classes and relative risks, if appropriate, will be presented.

For infections, time-to-event analysis will be done. Results will be tabulated and the Kaplan-Meier estimates for the cumulative rate will be plotted.

Additional analyses will be provided for adjudicated adverse events.

In supplementary analyses, exposure (or observation)-time adjusted analyses in terms of incidence rate and event rate will be provided.

Laboratory data

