Note: any AIN457 300mg (including AIN457 150mg FI switch to AIN457 300mg FI, AIN457 300mg FI, AIN457 150mg SoR switch to AIN457 300mg FI, AIN457 300mg SoR, AIN457 300mg SoR switch to AIN457 300mg FI and AIN457 300mg OL); any AIN 150mg (including AIN457 150mg FI and AIN457 150mg SoR); Any AIN457 including all the groups above.

The following study periods will be considered for analysis:

- **Extension study period:** Week 52 post-dose to Week 268;
- **Entire study period:** Combination of Induction (in A2304 core) period + Maintenance (in A2304 and in A2307) period + Core follow-up period (consider only for subjects who enter E1 after core follow-up period) + Treatment period in E1 [Initial Randomization in A2304 core to week 268] (including follow-up period);
- **Entire treatment period:** Combination of Induction (in A2304 core) period + Maintenance (in A2304 and in A2307) period + Core follow-up period (consider only for subjects who enter E1 after core follow-up period) + Treatment period in E1 [Initial Randomization in A2304 core to week 260]
- **Follow-up 2 period:** after W268 visit to end of the study.

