### **1.6 Study medication**

The analysis of study treatment data will be based on the safety set.

The number of planned and actual injection number will be summarized by yearly interval (analysis visit) for entire treatment period and treatment group AIN457 150 mg FI and AIN457 300 mg FI.

In case it cannot be identified from the data collected or assumed from the planned treatment whether an injection contained placebo or secukinumab, it will be assumed that the syringe contained secukinumab. For example this applies to the 150 mg secukinumab treatment group (in which subjects should receive both an active and a placebo injection) if only one injection is given. If the medication pack number is not available, it will be assumed that the secukinumab injection was applied. If this scenario occurs for subjects in the 300 mg treatment group when subjects should receive two identical injections, it will be assumed that they received secukinumab as planned.

The duration of exposure to study drug will be summarized by treatment group and yearly interval for entire treatment period.

Duration of exposure will be defined and summarized as follows:

For extension study period, duration of exposure will be defined as the time from first dose of study medication in extension 1 to the end of treatment period in extension 1 study; and for entire study period duration of exposure will be defined as the time from first dose of study medication in core study to the end of treatment period in extension 1 study. The end of treatment period will be defined as the last dose plus 84 days or last visit whichever occurs earlier. i.e., for subjects who discontinued or have their last visit earlier than last dose plus 84 days, the end of study treatment exposure will be the date of the last study visit in the corresponding treatment period.

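### SAP 1.9.1 cuts the protocol's 84-day treatment-emergent window at the last follow-up visit, and SAP 1.1.1 does not declare the change

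*SAP*

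**What the plan says.** **Protocol 9.5.2 (Safety variables).** Treatment-emergent events are "any events started after the first dose of study treatment and within 84 days after the last study treatment", plus earlier events that worsen within the same 84 days. No visit date enters the rule. The next paragraph begins "With the exception of adverse events that qualify as" treatment emergent, and sends all other telephone and unscheduled-visit data from Follow-up 2 to listings only. Treatment-emergent events learned of in Follow-up 2 therefore belong in the summary tables.

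**SAP 1.9.1 (Adverse events).** The window must be met "within last dose + 84 days or last visit date of follow-up 1 period which comes earlier". The same paragraph adds: "Only treatment emergent adverse events are summarized". Other events appear in listings with a treatment-emergent flag, and are summarised only if someone asks.

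**SAP 1.1.1 (Changes to statistical methods).** Three changes are listed: the PASI area table, the handling of missing data for maintenance of response, and an added by-year adverse event analysis. The shorter window is not one of them.

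**Data collection.** Protocol Section 6 says that, as a minimum, "subjects will be contacted for safety evaluations during the 12 weeks following the last dose of study treatment", by telephone or letter if the subject does not return. Protocol 7.2 requires SAE reporting to 12 weeks after the last dose or 30 days after the end of participation, or to the last telephone contact for subjects in Follow-up 2.

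**Exposure.** For subjects who leave before last dose + 84 days, SAP 1.6 states that "the end of study treatment exposure will be the date of the last study visit in the corresponding treatment period". The censoring rule in SAP 1.9.1 uses a similar minimum.

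**The concern.** The primary objective is long-term safety, and the treatment-emergent definition decides which events reach its tables. The SAP makes that definition narrower than the protocol's without saying so.

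The events at risk are not a random sample. A subject who becomes too ill to attend, or who dies, has the event after the last visit. For laboratory, vital-sign and ECG data a visit limit costs little, because those data arise at visits. Adverse events do not, and the protocol sets up contact and SAE reporting to capture those that start between or after visits.

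**Working it through.** **1. The plan's own timing.** The last dose is at Week 256, study day 1793. Protocol Table 6-1 and SAP Table 1-8 give:

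- Week 260 (end of treatment): 1821 − 1793 = 28 days after last dose
- Week 264 (first follow-up visit): 1849 − 1793 = 56 days
- Week 268 (last follow-up visit): 1877 − 1793 = 84 days

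Protocol Table 15-1 agrees: 672/24 = 28 days and 2016/24 = 84 days. The planned Week 268 visit falls exactly at the end of the protocol window.

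**2. Days lost.** Let g be the days from last dose to the last follow-up-1 visit. The protocol window is 84 days, the SAP window is min(84, g), and the loss is 84 − min(84, g).

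| Last follow-up-1 visit | g | Days lost | Share of 84 |
|---|---|---|---|
| Week 268 on schedule or later | ≥ 84 | 0 | 0% |
| Week 268, 5 days early | 79 | 5 | 6% |
| Week 268, 5 days early, and last dose 5 days late | 74 | 10 | 12% |
| Week 264 | 56 | 28 | 33% |
| None | undefined | depends on reading | – |

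The second and third rows assume that the ±5-day window applies to follow-up visits. The sentence on this in Protocol Section 6 is garbled but mentions the follow-up period.

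**3. No follow-up-1 visit.** Week 260 belongs to the treatment period (Protocol 3.1), so a subject last seen at end of treatment has no follow-up-1 visit and SAP 1.9.1 gives no cut-off. If the 84-day limit alone applies, nothing is lost. If the last-visit rule for exposure is borrowed, 84 − 28 = 56 days are lost (67%). The SAP does not say which.

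**4. What that could mean in events.** The documents give no event rates, so the rates here are assumptions, held constant over time. Expected events lost per 100 such subjects = 100 × (days lost / 365.25) × rate per patient-year.

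| Days lost | SAEs at 5–10 per 100 patient-years | AEs at 1–3 per patient-year |
|---|---|---|
| 5 | 0.07–0.14 | 1.4–4.1 |
| 10 | 0.14–0.27 | 2.7–8.2 |
| 28 | 0.38–0.77 | 7.7–23.0 |
| 56 (borrowed rule) | 0.77–1.53 | 15.3–46.0 |

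These are events, not subjects. Many subjects will already have had some adverse event over the years of treatment, so the percentage with any AE should move little. Tables of SAEs, deaths and rare events are more exposed.

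**5. Crude incidence against rates.** Crude incidence is x/n (SAP 2.3.1). The rule lowers x and leaves n unchanged, so the estimate can only fall. The exposure-adjusted rate is D/T (SAP 2.4.1). There D and T are cut together, so the bias is small unless the risk is higher after the last visit than before it.

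**The case against.** **The SAP sentence is loose.** Its end limit could be read as applying only to worsened pre-existing events. That reading leaves new-onset events with no end limit at all, which also departs from Protocol 9.5.2. SAP 1.4.6 and 1.9.2 use the same minimum and favour the plain reading.

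**The consequences are limited.** This stands. The events stay in flagged listings, SAE reporting to the sponsor is untouched, no hypothesis is tested, and subjects who discontinue treatment are directed to the same Week 260, 264 and 268 visits.

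**Stronger readings that the documents do not support:**

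- A reader might infer that the protocol's Follow-up 2 exception becomes void, because the SAP starts that period "after W268 visit to end of the study". But the SAP rule tests the date of onset, not when or how the event was reported. An event that starts on day 70, with Week 268 on day 84, is treatment emergent under the SAP even if first reported in a Follow-up 2 call. Subjects entering Follow-up 2 should also have attended Week 268, at about day 84, and later onsets are not treatment emergent under the protocol either.
- A reader might infer that a death on treatment between site visits up to 16 weeks (112 days) apart is excluded. SAP 1.9.1 names the last follow-up-1 visit, not the last site visit. The exposure rules say when person-time ends, not which events count, and for a subject with an event they end it at onset.
- A reader might take the roughly 108 of 675 subjects (16%) who had discontinued by Amendment 1 as the number affected. That is a count of discontinuations, not of subjects whose last follow-up-1 visit came before day 84.

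**Conclusion.** The point holds. The SAP's treatment-emergent window is shorter than the protocol's for any subject whose last follow-up-1 visit falls before day 84, it has no rule for a subject without such a visit, and the change is not declared. The loss is nil for subjects seen on schedule at Week 268, 5 to 10 days for an early Week 268 within the windows, and 28 of 84 days when Week 264 is the last follow-up-1 visit. The 56-day figure applies only if the exposure rule is borrowed for subjects with no follow-up-1 visit.

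The total effect cannot be sized, because the number of such subjects is not given. It is probably small in the overall AE percentages. It matters most for SAE and death counts and for crude incidence, where the excluded events are likely to be the ones that kept a subject from returning. This rests on reading the end limit as covering new-onset as well as worsened events.

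**What to change.** In SAP 1.9.1, define treatment emergent as onset or worsening after the first dose and on or before last dose + 84 days, whatever the last visit date and whatever the source of the report, including telephone contact and Follow-up 2. In SAP 1.4.6, 1.6 (text and formula) and the censoring rule in 1.9.1, end person-time at the earlier of last dose + 84 days and the date of last contact or death. Keep the existing censoring at treatment switch and at the end of each yearly interval.

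If the sponsor prefers the visit limit, the least that is needed is to declare and justify it in SAP 1.1.1, state the rule for subjects with no follow-up-1 visit, and add a sensitivity table under the protocol window.

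The cost is small programming changes in several SAP sections and slightly higher reported AE counts. No new data are needed. An extra summary table of non-treatment-emergent Follow-up 2 events is not part of this fix: Protocol 9.5.2 assigns those to listings.

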7.2 Serious adverse event reporting

To ensure patient safety, every SAE, regardless of causality, occurring during following time periods must be reported to Novartis within 24 hours of learning of its occurrence:

- after the subject has provided informed consent and until 12 weeks after the last administration of study treatment or 30 days after the subject has stopped the study participation (defined as last visit of the study at Week 268) for subjects who don't enter follow-up 2 period
- after the subject has provided informed consent and until the last telephone contact for patients who enter follow-up 2 period

Any SAEs experienced after these periods should only be reported to Novartis if the investigator suspects a causal relationship to study treatment.

Recurrent episodes, complications, or progression of the initial SAE must be reported as follow-up to the original episode, regardless of when the event occurs. This report must be submitted within 24 hours of the investigator receiving the follow-up information. An SAE that is considered completely unrelated to a previously reported one should be reported separately as a new event.

Information about all SAEs (either initial or follow up information) is collected and recorded in English on the paper Serious Adverse Event Report Form or the electronic Serious Adverse Event Form within the OC/RDC system (where available). The Investigator must assess the relationship to each specific component of the study treatment (if the study treatment consists of several components).

SAEs (initial and follow-up) that are recorded *on the paper SAE form* should be faxed **within 24 hours of awareness** of the SAE to the local Novartis Drug Safety and Epidemiology Department. The telephone and fax number of the contact persons in the local department of Drug Safety and Epidemiology, specific to the site, are listed in the investigator folder provided to each site. The original copy of the SAE Report Form and the fax confirmation sheet must be kept with the case report form documentation at the study site. Follow-up information should be provided using a new paper SAE Report Form stating that this is a follow-up to a previously reported SAE

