### **1.4 Assessment windows, baseline and post baseline definitions, missing data handling**

#### **1.4.1 Assessment windows**

No assessment windows have been defined for this study. Visit windows are described below.

If not otherwise specified, ‘first dose’, ‘randomization’ and ‘baseline’ are with respect to core study.

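### The extension-only adverse event tables exclude core-onset events with no exception for those that worsen on extension treatment, an undeclared departure from the protocol's treatment-emergent definition

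*SAP*

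**What the plan says.** - **SAP 1.9.1, extension tables.** The rule is that adverse events which "started in core studies before the first dose of the study treatment in extension and continued into extension will not be included" in the on-treatment E1 tables. The sentence does not mention worsening.
- **SAP 1.9.1, treatment-emergent definition.** This does include worsening: it covers "events present prior to the first dose of study medication but increased in severity after dosing based on preferred term".
- **SAP 1.4.1.** Unless otherwise specified, the terms first dose, randomization and baseline "are with respect to core study".
- **Protocol 9.5.2.** Treatment-emergent events include "events present prior to the first dose of study treatment, but increased in severity based on preferred term within 84 days" of the last study treatment.
- **Protocol 3.1, 5.5.4 and 9.1.** The Week 52 dose is the first of the extension treatment period, and first administration of study treatment is at Week 52. The safety set is defined by dosing in the treatment period, which runs from Week 52 to Week 260.
- **SAP 1.9.1, yearly intervals.** In the exposure-time rule, "worsening is not considered between the yearly interval". Yearly adverse event summaries are specified for the 150 mg and 300 mg fixed-interval cohorts only.
- **SAP 1.9 and 1.9.1, other outputs.** Frequencies and rates are also given for the entire treatment period (core plus extension), and all adverse events are listed over the entire study period.
- **SAP 1.1.1.** The listed changes from the protocol include the added one-year-interval analysis. They do not include any change to how worsened events are counted.

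**The concern.** The primary objective is long-term safety in subjects who completed the core studies. The E1 tables are the summaries that isolate the extension. For the start-of-relapse and open-label groups they are the only planned extension-specific adverse event summaries, because the yearly rows cover only the fixed-interval cohorts.

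Several categories that matter here can start mild and progress. SAP 1.9.1 names inflammatory bowel disease and cardio-cerebrovascular events as special-interest categories. The regulator's commitment quoted in protocol Amendment 2 names gastrointestinal and cardiovascular events. If such an event begins in the core year and becomes severe in the third year of treatment, the protocol's definition makes it an extension safety finding. The SAP's exclusion, read literally, keeps it out of the extension tables.

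**Working it through.** This is a conflict between counting rules, so the main check is to follow one event through each rule. Take an adverse event that starts mild in the core study, is still ongoing at Week 52, and becomes severe in the extension within 84 days of the last dose.

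1. **Protocol 9.5.2.** With the first dose of study treatment at Week 52 (protocol 3.1 and 5.5.4), the event was present before that dose and later increased in severity. It is treatment-emergent.
2. **SAP 1.9.1, worsening clause.** With the first dose taken as the core dose (SAP 1.4.1), the event was not present before first dose. It is treatment-emergent by its core onset, and the worsening clause does not apply.
3. **SAP 1.9.1, E1 exclusion.** The event started in the core study and continued. It is left out of the E1 tables.
4. **SAP yearly rows (fixed-interval cohorts).** On a single record the event counts in the year of onset only.
5. **SAP entire-treatment-period tables and listings.** The event is included. No output is specified that shows the worsening fell in the extension.

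Steps 1 and 3 give different answers for the same event, and SAP 1.1.1 does not declare the difference.

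**What the result depends on.** Step 3 assumes that the worsening stays on the original record. Protocol 7.1 requires changes in severity to be assessed at each visit but does not say whether a worsening opens a new record with its own start date. If it does, the new record has an extension onset and the E1 exclusion does not catch it.

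**Direction.** Let k be the number of subjects whose only qualifying extension event is a worsened core-onset event.
- Crude incidence (SAP 2.3.1) is x/n. Under the exclusion it becomes (x − k)/n, a relative shortfall of k/x.
- The exposure-adjusted rate (SAP 2.4.1) is D/T. Under the exclusion it becomes (D − k)/(T + Δ) with Δ ≥ 0, because these subjects go on accruing event-free time. This is below D/T whenever k > 0.

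Both measures move downward relative to the protocol definition.

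**Size.** The documents give no value for k, so the shortfall cannot be computed. The only planned detection figure is in protocol 9.7, and it reproduces:
- 918 × 0.95 × 0.85 = 741.3 (stated about 740); 741.3 × 0.80 / 4 = 148.3 (stated about 148 per group).
- 1 − (1 − 0.001)^148 = 13.8% (stated about 14%); 1 − (1 − 0.01)^148 = 77.4% (stated about 77%).

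As an illustration only, assume that a share f of affected subjects qualify solely through a worsened core-onset event. The chance of at least one counted case in an extension-only table is then 1 − (1 − p(1 − f))^148:

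| f (assumed) | p = 0.1% | p = 1% |
|---|---|---|
| 0 | 13.8% | 77.4% |
| 5% | 13.1% | 75.7% |
| 10% | 12.5% | 73.8% |
| 20% | 11.2% | 69.5% |

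The values of f have no source in the documents. The entire-treatment-period tables lose nothing at any f.

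**The case against.** **The events are still reported.** Core-onset events are counted in the entire-treatment-period tables, with the greatest severity shown where a subject reports the same preferred term more than once. They are also listed over the entire study period. This stands, and it rules out the inference that late safety events are lost from the report. What is missing is narrower: the whole-period outputs merge the core year with the extension and are not set up to show when a worsening occurred.

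**The SAP is internally consistent.** With first dose meaning the core dose, an event arising on core treatment is already treatment-emergent and is counted once. This also stands, so the conflict is not within the SAP. It is between the SAP and protocol 9.5.2, and it depends on reading the protocol's first dose as Week 52. Protocol 9.5.2 does not repeat that definition, but protocol 3.1, 5.5.4 and 9.1 all support it.

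**The yearly rows are a declared addition.** SAP 1.1.1 lists them, the protocol has no yearly rule to depart from, and counting new onsets only is a recognisable convention. This stands. The rows need a clear label, not a correction.

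**Recurrent serious events.** A reader might infer that a serious event from the core year that recurs in the extension is also excluded, because protocol 7.2 says "Recurrent episodes, complications, or progression of the initial SAE must be reported as follow-up to the original episode, regardless of when the event occurs". The documents do not support this. That rule governs 24-hour reporting to the sponsor and does not set an onset date for analysis. An event that resolved and then recurred has not continued into the extension, so the wording of the E1 exclusion does not reach it.

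**Feasibility.** The SAP covers the final analysis, and SAP 1.12 records four interim analyses already done. Dated severity changes may not have been captured. That is a fair limit on the remedy, and the fix allows for it.

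**Conclusion.** The point holds for the extension-only tables. As written, SAP 1.9.1 leaves out a continuing core-onset event that worsens on extension treatment, although protocol 9.5.2 counts it as treatment-emergent, and SAP 1.1.1 does not declare the departure. Relative to the protocol definition, the bias in E1 incidences and rates is downward. The documents give no basis for a figure.

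The conclusion rests on two assumptions: that the protocol's first dose of study treatment is the Week 52 dose, which its own sections support, and that a worsening is not entered as a new adverse event record, which the documents leave open. The whole-period tables and listings are unaffected, and the point does not extend to recurrent serious events. The gap is worth closing because the E1 tables serve the primary objective and the change is small.

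**What to change.** - **SAP 1.9.1, exclusion rule.** Replace it with wording to this effect: *an adverse event that started in the core study and was ongoing at the first extension dose is excluded from the E1 tables unless its severity increased, by preferred term, after that dose; if so, it is counted in the E1 tables with the date of worsening as its onset.* Keep the criterion to severity, to match protocol 9.5.2, and leave the end of the treatment-emergent window as it is.
- **If dated severity changes are not available.** Give a separate count and listing of core-onset adverse events that worsened in the extension, by treatment group.
- **Yearly fixed-interval rows.** Add a footnote that they count new onsets only, or show worsened events alongside.
- **SAP 1.1.1.** Declare the rule adopted, including any remaining departure from protocol 9.5.2.

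No change to the serious adverse event reporting rules is needed on this ground. The cost is SAP wording and some extra derivation, with no new visits. E1 incidences may come out slightly higher.
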